5.7 Primary Endpoint Analysis

The primary endpoint measure is the change in the Energy and Vitality subscale of the SF-36 questionnaire from baseline (i.e., pre-treatment) to 3 months post-randomization. It is a continuous variable.

The primary endpoint will be analysed using a mixed-effects repeated measures model to account for missing values. The model will be set up as follows: The Energy and Vitality subscale is the dependent variable, visit (baseline and month 3) is the repeated measure (a fixed effect), subject and site are random effects (with subject nested in site) and treatment group by visit is a fixed effect. In the case that the primary endpoint was not homogeneous across study sites (as discussed in Section 5.3), a treatment by visit by site interaction will also be included in the primary endpoint model as a random effect. Results will be presented as the mean difference in the change score from baseline to 3 months (adjusted for baseline score, as appropriate) between the two treatment groups with a 95% confidence interval at 3 months and p-value for the treatment group effect.

As a sensitivity analysis of the primary endpoint, a similar mixed-effects repeated measures model to the above will be constructed, that also adjusts for other baseline and demographic variables that were found to be imbalanced between treatment groups per Section 5.6. The mean difference in change score from baseline to 3 months will be presented with a 95% confidence interval at 3 months.

For these analyses of the primary endpoint, a P-value of less than 0.05 will be used to indicate statistical significance. Analyses of the primary endpoint will be generated for the ITT-1 population.

A second sensitivity analysis for the primary endpoint will be generated using the CC-1 population.

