4.2 Enrolment Target and Inclusion/Exclusion Criteria

The MERGE study is a prospective multicentre randomised parallel trial with 3 months of active treatment versus a control arm. Randomisation with minimisation will be performed with a 1:1 treatment group allocation.

Date of start of recruitment:	26 October 2016
Date of expected end of recruitment:	31 December 2018
Date expected end follow-up:	31 March 2019
Target number of subjects:	224 (112 per arm)
Participating Centres:	11

A patient will be eligible for inclusion in the study if all the following inclusion criteria apply:

- AHI 5-15 events/hr as per AASM 2007 scoring criteria or AHI ≥ 5 per AASM 2012 if AHI 0-4.9 per AASM 2007
- Aged ≥ 18 and ≤ 80 years
- Ability and willingness to provide written informed consent
- Ability to tolerate a CPAP one hour long run-in test

A patient will not be eligible for the study if any of the following exclusion criteria apply:

- The presence of unstable cardiac disease at trial screening
- Inability to give fully informed consent
- Use of supplemental oxygen
- Secondary sleep pathology e.g. Periodic Limb Movement Syndrome, Narcolepsy, Circadian Disorder, Obesity Hypoventilation Syndrome
- Epworth Sleepiness Scale (ESS) ≥ 15 , or concerns about sleepy driving from physician/ sleep lab staff
- Body Mass Index (BMI) $\geq 40 \text{ kg/m}^2$
- Previous CPAP usage

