4.6 Sample Size

The sample size of 224 (112 per arm) is based on statistics observed in the MOSAIC study: a mean score difference of 6.6 was observed between 3 months and baseline (considered a significant clinical improvement by the authors of the study) in the Energy and Vitality subscale of the SF-36 questionnaire, with a mean change of 4.2 (SD 18.1) in the Control group and 10.8 (SD 17.0) in the CPAP Treatment group. The sample size calculation is based on a two-sided 5% significance level and 80% power.

It is estimated that approximately 300 participants will need to be randomised in order to reach the required sample size of 224 patients with mild OSA **per AASM 2012 guidelines**. Subjects who are eligible for Home Sleep Testing (HST) are evaluated for their level of OSA. Those patients who have Mild OSA **per AASM 2007 guidelines** are eligible for randomisation. Those patients who have No OSA **per AASM 2007 guidelines** are further assessed based on the AASM 2012 guidelines. All patients with

AHI \geq 5 per AASM 2012 guidelines are also eligible for randomisation. Since the primary endpoint analysis is based on patients with mild OSA per AASM 2012 guidelines, there will be some patients randomised who will not fall into this sample, thus the need for additional enrolment. Additionally, it is expected that 10% of those randomised will drop-out before the end of the study.

The number of patients required to enrol will be reviewed and updated by the Trial Steering Committee (TSC) as new recruitment information accumulates. This will not change the goal of 224 patients completing the study who had mild OSA per the AASM 2012 guidelines.

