5.6 Comparability Analysis of Baseline Characteristics

Patients in the two treatment groups will be compared with respect to baseline and demographic characteristics (e.g., ethnicity, medical history), minimisation factors for randomisation (i.e., gender, age, BMI), and baseline quality of life endpoints for the ITT-1 population.

Baseline sleep test parameters will be compared by treatment group for the ITT-1 and ITT-2 populations.

Descriptive statistics within each treatment group will be presented for demographic and baseline values. For binary and categorical variables, the number evaluated, counts (with percentages) and 95% exact confidence limits for the percentage will be presented. For continuous variables, the number evaluated, mean, standard deviation, median, minimum, maximum, and 95% confidence interval for the mean will be presented. Treatment groups will be compared with respect to baseline variables in order to test that the groups are balanced. For continuous variables, a student's t-test or Wilcoxon rank sum test will be used, as appropriate. For categorical and binary endpoints, Fisher's exact test will be utilized. All tests will be tested using a Type I error rate of 0.05.

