8. AMENDMENT

Amendment to SAP Version 1.4

Effective as of: 19Jun2019

Changes and additions to planned analyses

5.7 – 5.8 Primary and Secondary Endpoint Analyses

SAP version 1.4 specified a mixed-effects repeated measures model as the primary analysis for the

primary endpoint; the primary analysis population was the ITT-1 population. Sensitivity analyses of the primary endpoint, as well as all analyses of secondary endpoints, were also specified using the mixed-effects repeated measures model; the analysis populations of interest were the CC-1 and CC-2 (completed case) populations.

After reviewing preliminary results, the Trial Steering Committee determined that it would be more appropriate to examine endpoints in a true intent-to-treat fashion, including all patients in the analyses, rather than focusing on completed cases.

The primary analysis of the primary endpoint was performed as specified. For sensitivity and secondary endpoint analyses, the mixed-effects repeated measures analysis was replaced with analysis of covariance (ANCOVA) in the ITT-1 and ITT-2 analysis populations. The ANCOVA model adjusted for baseline score, where missing 3-month scores were replaced with baseline scores using a last observation carried forward (LOCF) approach. The advantages of using the ANCOVA LOCF model were (1) it was considered a conservative method of handling missing data, in which patients would have seen no improvement had they remained in the trial, and (2) this approach had the benefit of simplifying the underlying model assumptions.

Secondary endpoints were also analyzed using the ANCOVA LOCF model for the group of patients with no OSA (AHI<5) per **AASM 2007 guidelines** but who entered the study (AHI \geq 5) per **AASM 2012 guidelines**; these patients were considered the “very mild” group.

Additionally, effect sizes were calculated for each analysis model as

$$\text{effect size} = \frac{\text{treatment difference}}{\text{pooled SD}}$$

where

treatment difference = adjusted mean treatment difference (CPAP – SC) from analysis model

pooled SD = $\text{SE}_{\text{trt diff}} / \sqrt{\left(\frac{1}{n_{CPAP}}\right) + \left(\frac{1}{n_{SC}}\right)}$ for mixed effects model

pooled SD = root MSE for ANCOVA LOCF model.

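### Neither the SAP 5.7 model nor its section 8 replacement, read plainly, gives a working check on imbalance in covariates other than baseline vitality

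*SAP*

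**What the plan says.** SAP 5.7 models the vitality score at baseline and month 3, with visit and treatment-by-visit as fixed effects and subject within site as random effects. Its first sensitivity analysis is a similar model "that also adjusts for other baseline and demographic variables that were found to be imbalanced between treatment groups per Section 5.6", and the quantity reported is again the difference in change score. The form in which covariates enter is not given.

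SAP 5.6 decides what counts as imbalanced: "Treatment groups will be compared with respect to baseline variables in order to test that the groups are balanced", by t-test or Wilcoxon test and Fisher's exact test, each at 0.05. The variables include demographics, the minimisation factors and the baseline quality-of-life scores.

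SAP section 8 (effective 19 June 2019, after preliminary results were reviewed) keeps the primary analysis. For sensitivity and secondary analyses it substitutes an ANCOVA with missing month-3 scores replaced by baseline scores. On covariates it says "The ANCOVA model adjusted for baseline score" and names no others.

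**The concern.** A covariate-adjusted sensitivity analysis should show whether the treatment effect changes once chance differences between arms are allowed for. That requires the covariate to act on the change from baseline. In a model whose outcome is the score at both visits, a fixed covariate added as a main effect acts on the level and not on the change. The adjusted result would then match the primary result almost automatically, and the match would say nothing about imbalance. The section 8 ANCOVA could carry such covariates properly but lists only the baseline score.

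The selection rule is a separate problem. A significance test between randomised arms measures how surprising a difference is, not whether the variable predicts change in vitality. It can admit irrelevant variables and leave out prognostic ones.

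At stake is the value of the robustness check on the primary result, not the primary result itself.

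**Working it through.** **Inputs.** From SAP 4.6: "a mean change of 4.2 (SD 18.1) in the Control group and 10.8 (SD 17.0) in the CPAP Treatment group"; difference 6.6; "The sample size calculation is based on a two-sided 5% significance level and 80% power"; 10% dropout; "The sample size of 224 (112 per arm) is based on statistics observed in the MOSAIC study". From SAP 4.2: "Randomisation with minimisation will be performed with a 1:1 treatment group allocation". Model forms are from SAP 5.7 and section 8; test level from SAP 5.6.

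**Step 1: the plan's own figure.** Pooled SD = √((17.0² + 18.1²)/2) = 17.56. Per arm, n = 2 × (1.960 + 0.842)² × 17.56² / 6.6² = 111.1, rounded up to 112, so 224 in total. This reproduces the SAP (power 80.3% at 112 per arm). Nothing below alters it.

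**Step 2: algebra for 5.7.** With v = 0 or 1 for visit, T for arm and x for a baseline covariate as a main effect:

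E(Y) = a + b·v + g·T + d·T·v + c·x

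Month 3 minus baseline is b + d·T, so c·x cancels and d is unchanged. Adding a term h·x·v makes the change b + d·T + h·x, and d is then adjusted for x.

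**Step 3: numerical check of 5.7.** One simulated complete data set (112 per arm, subject within site random) gave:

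- no covariate: 9.0739, SE 2.268, equal to the raw difference in change;
- covariate as main effect: 9.0739, SE 2.268;
- covariate-by-visit: 7.65, SE 2.287.

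Then 150 simulated trials per scenario were run with a subject random intercept. Assumptions not in the documents: one covariate imbalanced by 0.3 SD, worth 4 points per SD at baseline and 4 more on the change; true effect 6.6; scores missing completely at random. Mean estimates:

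| Model | Complete | 10% of month-3 scores missing |
|---|---|---|
| Mixed model, no covariate | 7.71 | 8.04 |
| Mixed model, covariate main effect | 7.71 | 8.04 |
| Mixed model, covariate-by-visit | 6.50 | 6.89 |
| ANCOVA, baseline score only | 8.29 | 7.60 |
| ANCOVA, baseline score and covariate | 6.71 | 6.20 |

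Columns are separate simulated sets, so compare down and not across; simulation error of a mean is about 2.4/√150 = 0.2. The main effect moved individual estimates by a mean of 0.09 points at 10% missing and 0.12 at 20%, against standard errors of about 2.4 to 2.6. The covariate-by-visit shift with complete data, 7.71 − 6.50 = 1.21, matches the imbalance built in (0.3 × 4 = 1.2).

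**Step 4: section 8.** The last two rows show that ANCOVA on baseline score alone leaves the assumed imbalance in place, and that adding the covariate removes it (with complete data, 8.29 to 6.71 against a truth of 6.6).

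**Step 5: the selection rule.** Countable tests from SAP 4.7 to 4.9: 3 minimisation factors plus 18 baseline scores (10 SF-36, ESS, FSS, FOSQ, 2 HADS, ISI, EQ-5D index, VAS) = 21.

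- Expected chance flags: 21 × 0.05 = 1.05.
- Chance of at least one, if independent: 1 − 0.95²¹ = 66%.
- Smallest difference flagged at 112 per arm: 1.96 × √(2/112) = 0.26 SD.
- A 0.25 SD difference: z = 0.25/√(2/112) = 1.87, p = 0.06, not flagged.

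**The case against.** A reader might infer that the planned analysis is incapable of correcting imbalance, or agrees with the primary analysis by construction. The documents do not support that. SAP 5.7 leaves the covariate form open, and a covariate-by-visit term would be adjustment in the ordinary sense and would work. Cancellation is exact only with complete data, whereas the ITT-1 population will have missing scores. It also fails under a common-baseline constraint (mean 8.35 without the covariate, 7.69 with it), but 5.7 does not state one.

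A reader might also infer that section 8 withdraws the adjustment. It is silent: it changes the model and the missing-data rule and neither keeps nor drops the other covariates. It does correct imbalance in baseline vitality. The selection problem depends on that silence, because if no further covariates are used the 5.6 tests select nothing. Nor does the SAP present this analysis as proof against imbalance; it calls it a sensitivity analysis.

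The size of any shift is open to challenge. For unadjusted change, a 0.25 SD imbalance with an assumed correlation of 0.2 to 0.4 with change gives 0.2 × 0.25 × 17.56 = 0.9 to 0.4 × 0.25 × 17.56 = 1.8 points. That range need not carry over to the ANCOVA. Suppose FSS correlates −0.5 with baseline vitality, the two vitality scores correlate 0.5 with equal variances, and FSS has no effect of its own. Then FSS correlates −0.25 + 0.5 = 0.25 with change, yet adjusting for baseline score removes it entirely.

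Finally, minimisation on gender, age and BMI limits imbalance in those factors. That holds across all those randomised (about 300), not necessarily within the mild AASM 2012 subset of 224 used for the primary analysis.

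These points narrow the claim. They do not supply a working check: followed as written, 5.7 gives near-identity and section 8 gives adjustment for baseline score only.

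**Conclusion.** The concern holds in limited form. On the plain reading, neither 5.7 nor section 8 contains a sensitivity analysis that corrects the effect on change for imbalance in covariates other than baseline vitality. The 5.7 result rests on covariates entering as main effects, treatment-by-visit without a common-baseline constraint, and little missing data. The section 8 result rests on its wording, which leaves the matter unstated.

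The selection rule in 5.6 and 5.7 is unsound if the adjustment is kept. The count of 21 is inferred from the SAP, which also mentions ethnicity and medical history. The 66% assumes independent tests, which related questionnaire scores will not be.

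The simulated shifts are illustrative because the documents give no covariate effects. The primary analysis and the target of 224 stand. This should be corrected, but it does not threaten the main result.

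**What to change.** State in section 8 that the covariate-adjusted sensitivity analysis is kept. Specify it as the month-3 ANCOVA on baseline score plus a fixed short list chosen by design or prognosis, whatever the baseline p-values: the minimisation factors gender, age and BMI, and optionally baseline AHI, ESS and FSS. The equivalent within 5.7 is to add covariate-by-visit terms for the same list.

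Delete selection by the 5.6 tests and make 5.6 descriptive. Disclose that the list was set after preliminary results were reviewed.

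The cost is SAP wording, one extra model run on data already collected and a few degrees of freedom. The list can no longer be called fully pre-specified. Using the minimisation factors as its core limits that drawback, since they were fixed at randomisation.

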5.8 Secondary Endpoint Analyses

A mixed-effects repeated measures model will be utilized to compare treatment groups for all

secondary endpoints to account for missing values, as needed. The model will be set up as follows: The Secondary Endpoint subscale or total score is the dependent variable, visit (baseline and month 3) is the repeated measure (a fixed effect), subject and site are random effects (with subject nested in site) and treatment group by visit is a fixed effect.

Each secondary endpoint measure will be analysed in the same way as the primary endpoints for comparing the Treatment and Control groups using the CC-1 and CC-2 populations. Results will be presented as the mean difference in the change score (for each secondary endpoint) from baseline to 3 months (adjusted for baseline scores, as appropriate) between the two treatment groups with a 95% confidence interval at 3 months and p-value for the treatment group effect.

All secondary endpoints will be analysed separately for patients in the CC-1 and CC-2 populations. There will be no statistical testing of differences between the CC-1 and CC-2 populations.

There will be no formal adjustments for multiple significance testing. All secondary analyses will be considered exploratory. We will explicitly state that the study was not powered for statistical comparisons of secondary endpoints in study publications and will urge caution for the interpretation of results obtained using secondary endpoints.

5.9 Safety Analyses

Any adverse event occurring while a patient is continuing in the study through the 3-month visit will be recorded. A comparison of adverse events between the Treatment and Control groups will be assessed descriptively, presenting the number of events and percent of patients having one or more of each event type by treatment group. A listing of all adverse events reported during the study will be presented, including the event description, time of occurrence, severity, outcome, expectedness and relationship to the study treatment. The safety analysis will be conducted on the ITT population.

5.10 Additional Exploratory Analyses

All secondary endpoints will be summarized by treatment group and presented descriptively for the CC-3 population (CC patients diagnosed as Moderate to Severe OSA per AASM 2012 guidelines). Descriptive statistics for the mean change from baseline to the 3-month visit for each endpoint include sample size, mean, standard deviation, median, minimum and maximum values for each endpoint.

Changes in quality of life scores from baseline to 3 months will be compared between Treatment and Control groups for patients with no OSA (AHI<5) per **AASM 2007 guidelines** but who enter the study (AHI \geq 5) per **AASM 2012 guidelines**. Descriptive statistics will be presented for the CC-1 population, and include sample size, mean, standard deviation, median, minimum and maximum values for each endpoint.

All secondary endpoints will be evaluated for the CPAP Treatment group, comparing patients in the Treatment group who are adherent to CPAP and not adherent to CPAP using descriptive statistics. No statistical inference will be made comparing these two groups and the results will be presented separately for patients in the CC-1 and CC-2 populations. Separate analyses will be presented for each definition of CPAP adherence.

Adherence to CPAP in the Treatment group will be further explored using logistic regression to assess the impact of baseline characteristics, OSA severity and other potential factors that predict compliance.

Usage data downloaded from the CPAP machines will also be summarized for all patients in the Treatment group over the 3- month study period, including residual AHI, mean usage hours per day, % of days with more than 4 hours of usage, median 95th percentile mask leak and % of patients using the myAir application. Additionally, the number of phone calls, emails, patient visits, reasons for contacts and missed contacts will be summarized to assess the effort required to support CPAP adherence. Comparisons will be presented overall and by CPAP adherence for patients in the ITT-1 and ITT-2 Treatment group populations.

The primary endpoint measure (mean change in Energy and Vitality subscale) will be examined over the spectrum of baseline AHI scoring as a continuous variable to investigate trends in the relationship between the two variables. Scatter plots of baseline AHI versus the primary endpoint will be generated for each treatment group. Statistical modelling may be performed to describe any observed variation in treatment effect related to baseline AHI. The primary endpoint will also be examined for any relationship between treatment effect and age or baseline BMI, using the methods described for AHI. These summaries will be produced for the ITT-1 population.

Mean change in ESS and FSS will also be assessed for variation in treatment effect related to baseline AHI, age, or BMI, using the methods described for the primary endpoint.

The primary endpoint measure will also be compared over the spectrum of baseline ODI and RERA scoring in a similar fashion as above. Separate scatter plots will be generated for the Treatment group, distinguishing patients adherent and non-adherent to CPAP.

Baseline and demographic characteristics, AHI, and quality of life scores will be summarized descriptively by gender for the ITT-1 population. Changes in quality of life scores from baseline to 3 months will be summarized descriptively by treatment group and gender, and the effect of gender will be explored by including gender as a fixed effect in the analysis model described in Section 5.7.

Change from baseline to 3 months in weight and BMI will be summarized descriptively by treatment group for the ITT-1 population.

The reason for patient referral will be analysed, comparing the primary endpoint measure by reason for referral separately for each treatment group using descriptive statistics.

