## 5.8 Pilot Phase

In order to test the trial methodology, the trial will start with a pilot phase of 20 randomised participants. At this stage the steering committee will meet to review the following:

- Average CPAP compliance
- Trial methodology and flow

**Compliance to treatment is crucial for study to be able to demonstrate whether CPAP treatment yields improvements in mild patients.** In order for patients to experience quality of life benefits, it has been shown that at least 4 hours usage per night is required, with greater use associated with increased benefits. If, during the pilot phase, average compliance is lower than 4 hours per night, the protocol will be amended to include the use of a CPAP 3 day run in phase, in order to include only patients who are able to use the device for greater than four hours per night. Additional changes to the protocol may also be made based on findings from the pilot phase.

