4.4 Description of Adherence in Treatment Group

Adherence with CPAP in the Treatment group will be defined as follows. Patients in the Treatment group will be considered adherent to CPAP if the patient uses the device at least 4 hours per day on average during the 3-month study period.

The US Medicare definition for adherence will be considered as a secondary definition for exploratory analyses. By this definition, patients who use the device at least 4 hours per night for 70% of the nights during a 30-day period over the 3-month study period are considered adherent.

Adherence to CPAP will be monitored using ResMed AirView Remote Monitoring system. Daily usage data over the study period will be provided for analysis.

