7. PLANNED TABLES AND FIGURES

- Number of Subjects Randomized by Treatment Group and Site
- Patient Accountability Flow Chart, Overall and by Analysis Populations
- Reasons for Study Withdrawal by Treatment Group
- Protocol Deviations by Treatment Group
- Demographic and Baseline Characteristics by Treatment Group
- Comparability of Baseline Variables Across Sites
- Pool-ability analysis, Primary Endpoint Results by Site and Treatment Group
- Primary Endpoint Analyses
- Secondary Endpoint Analyses for CC with mild OSA per 2012 AASM Guidelines
- Secondary Endpoint Analyses for CC with mild OSA per 2007 AASM Guidelines
- Adverse Events by Treatment Group
- Secondary Endpoint Analyses for CC with moderate to severe OSA per 2007 AASM Guidelines
- Secondary Endpoint Analyses for CC with no OSA per 2007 AASM Guidelines but who enter the study per AASM 2012 Guidelines.
- Secondary Endpoint Analysis for Patients treated with CPAP comparing Patients Adherent and Non-Adherent to CPAP for CC with mild OSA per 2012 AASM Guidelines
- Secondary Endpoint Analysis for Patients treated with CPAP comparing Patients Adherent and Non-Adherent to CPAP for CC with mild OSA per 2007 AASM Guidelines
- Impact of Baseline Factors on Adherence to CPAP in Treatment Group
- AirView/CPAP Usage Data for Patients treated with CPAP, Overall and Comparing Patients Adherent and Non-Adherent to CPAP
- Number/Percent of Types of Contacts for Patients treated with CPAP, Overall and Comparing Patients Adherent and Non-Adherent to CPAP (+ types of interventions, problems)
- Primary Endpoint Analyses over Baseline AHI, Age, and BMI
- Secondary Endpoint (mean change in ESS and FSS) Analyses over Baseline AHI, Age, and BMI
- Association between Primary Endpoint and ODI and RERA Scores by Treatment Group and CPAP Adherence
- Baseline Demographic Characteristics, AHI, and Quality of Life Scores by Gender
- Secondary Endpoint Analyses by Treatment Group and Gender
- Summary of Change from Baseline in Weight and BMI by Treatment Group
- Primary Endpoint Summarized by Reasons for Patient Referral and Treatment Group

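### Predictors of CPAP adherence are modelled only as a yes/no outcome although hours of use are recorded; adding a model for mean hours would recover information at little cost

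*SAP*

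**What the plan says.** SAP 5.10 plans one model for who adheres to CPAP: "Adherence to CPAP in the Treatment group will be further explored using logistic regression to assess the impact of baseline characteristics", together with OSA severity and other candidate factors. The matching output in SAP section 7 is titled "Impact of Baseline Factors on Adherence to CPAP in Treatment Group".

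SAP 4.4 supplies the response. A patient is "considered adherent to CPAP if the patient uses the device at least 4 hours per day on average during the 3-month study period". The secondary definition, the US Medicare rule, concerns "patients who use the device at least 4 hours per night for 70% of the nights during a 30-day period". SAP 5.10 does not say which definition enters the logistic model, but both are yes/no.

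SAP 4.4 also says: "Daily usage data over the study period will be provided for analysis". SAP 5.10 uses the continuous data only in a descriptive summary, which includes "mean usage hours per day, % of days with more than 4 hours of usage". No model takes hours as the response.

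Protocol 5.8 makes two statements about hours in one sentence. At least 4 hours per night is needed for quality-of-life benefit, and this is said "with greater use associated with increased benefits".

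The amendment in SAP section 8 lists predictors of adherence among the analyses to be reported later. It does not change the method.

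**The concern.** In this model CPAP use is the response. After the cut, a patient averaging 0 hours counts the same as one averaging 3.9, and 4.1 counts the same as 8. By the protocol's own account, differences in use on either side of 4 hours can matter, and the data to model them will be in hand.

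Only the CPAP arm contributes: 112 patients in the planned primary population, or about 150 if all of the roughly 300 randomised are used. At that size, discarding information can turn a moderate predictor of use into a null result, and a null result could be read as evidence that baseline features do not predict CPAP use in mild OSA. The smaller adherence class also limits how many predictors a logistic model can carry. At 33% adherent, for example, it holds about 0.33 × 112 = 37 patients.

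This is separate from the planned comparison of quality-of-life change between adherent and non-adherent patients. There, use is the grouping variable.

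**Working it through.** **1. The plan's own figure.** The only sample size stated is for the primary endpoint (SAP 4.6): difference 6.6, SDs 17.0 and 18.1, two-sided 5%, 80% power.

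- Pooled SD = √[(17.0² + 18.1²)/2] = √308.3 = 17.56.
- n per arm = 2 × (1.96 + 0.842)² × 308.3 / 6.6² = 111.1, rounded up to 112.
- Power at 112 per arm is 80.3%.

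The stated 112 reproduces. No power is stated for the predictor analysis, so the rest is conditional.

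**2. Inputs for the predictor analysis.**

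- From the SAP: n = 112 (4.6), or about 300/2 = 150 under 1:1 allocation (4.2, 4.6).
- Assumed: roughly normal hours, one predictor with correlation r to hours, adherent share p, two-sided 5% test.

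**3. Information kept by the cut.** For a normal response split so that a share p is adherent, the fraction kept is φ(z_p)² / [p(1 − p)].

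- p = 0.50: 0.3989² / 0.25 = 0.64
- p = 0.60: 0.62
- p = 0.70: 0.58
- p = 0.80: 0.49

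At p = 0.50, 112 patients carry the information of about 0.637 × 112 = 71.

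**4. Worked case: n = 112, r = 0.25, p = 0.50.** Approximate power is Φ[√(n − 3) × atanh(r) − 1.96].

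- Hours: Φ(10.44 × 0.2554 − 1.96) = Φ(0.71) = 76%.
- Cut outcome: r becomes 0.25 × √0.637 = 0.1995, so Φ(10.44 × 0.2022 − 1.96) = Φ(0.15) = 56%.
- Loss: 20 points.

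**5. Simulation.** 6,000 trials per setting, linear regression on hours against logistic regression on hours ≥ 4 (likelihood-ratio test), 50 to 70% adherent:

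| n | r | Power, hours | Power, logistic |
|---|---|---|---|
| 112 | 0.20 | 56% | 36–40% |
| 112 | 0.25 | 75% | 53–56% |
| 112 | 0.30 | 91% | 69–75% |
| 150 | 0.20 | 70% | 48–51% |
| 150 | 0.25 | 88% | 65–71% |
| 150 | 0.30 | 96% | 81–86% |

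The loss over this grid is 10.5 to 22.5 points. Variations:

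- Wald instead of likelihood-ratio test: 11.7 to 24.4.
- Hours floored at 0 and capped at 9: 10.6 to 24.0.
- A 50:50 binary predictor: 10.3 to 23.1.
- Robust standard errors for the linear model, 33 to 67% adherent: about 12 to 22.

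**6. Outside that window.**

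- r = 0.10: about 4 to 9 points.
- r = 0.40: about 1 to 9 points.
- 80% adherent: up to about 31 points.

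**7. A different shape of use.** Suppose use is bimodal (low users near 1.2 h, regular users near 6 h) and the predictor acts only on which group a patient falls in, with n = 112. Logistic regression was then ahead by about 2 to 5 points (for example 78% against 74%). Once the predictor also had a graded effect within the groups, hours were ahead by 11 to 17 points.

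**The case against.** The strongest reply is that 4 hours is not an arbitrary cut. The first half of the Protocol 5.8 sentence gives a referenced reason for it, the pilot-phase rule uses it, and so does the therapist's monitoring trigger in Protocol 5.5.3. Asking who reaches 4 hours is a coherent question, and logistic regression answers it. This stands, and it is why the logistic model should stay. It does not explain why hours should go unmodelled, since the same sentence also describes a graded benefit.

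Second, the SAP Introduction says later exploratory analyses are not bound by the plan, so the trial team could fit a model for hours anyway. That is true. Naming the model beforehand still has value, because it avoids choosing between two responses after seeing both.

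Third, the power loss rests on inputs the documents do not supply, and near-normal hours with a linear effect favour the linear model. This also stands: the size and, in the purely bimodal case, even the direction depend on the assumptions.

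A reader might infer that a real predictor will probably be missed. The figures do not support that in general. With 112 patients, logistic power is below one half at r = 0.20 but 53–56% at 0.25 and 69–75% at 0.30.

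**Conclusion.** The concern holds in a limited form. SAP 5.10 models adherence only as a yes/no response while daily hours are available, and this discards information. The loss is about 11 to 23 points of power if hours are roughly normal, r is 0.20 to 0.30, n is 112 to 150 and 33 to 70% adhere. None of the correlation, the distribution or the adherent share is given in the documents. The loss is roughly 1 to 9 points at r = 0.10 or 0.40, and logistic regression can be slightly ahead under purely bimodal use.

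Two stronger readings go too far. One is that the logistic model is wrong or the 4-hour cut unjustified; the protocol gives a rationale for that threshold. The other is that the choice weakens the trial's findings; the analysis is exploratory, has no power target, is deferred to a later report, and leaves the primary and secondary comparisons untouched. This is a cheap improvement, not a defect that must be corrected.

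**What to change.** In SAP 5.10, before the deferred analysis is run, add a regression with mean nightly hours of use over the 3 months as the response, on the same predictors as the logistic model. Use robust standard errors and report the difference in mean hours per unit of each predictor with a 95% confidence interval. Keep the logistic model on the 4-hour definition alongside it, and say that the primary definition in SAP 4.4 is the one used.

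The cost is a sentence or two of text and one extra model on data already due for analysis. Robust standard errors correct the variance estimate; they do not repair a poor linear fit. The fit should therefore be checked if hours prove skewed or massed near zero.
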